Improving the safety of oral immunotherapy for cow's milk allergy

(The SOCMA Study)

Version 2.1 dated 11 December 2018

SPONSOR: Imperial College London

FUNDING: J.P. Moulton Charitable Foundation
Sociedad Española de Alergología e Inmunología Clínica (SEAIC)
Sociedad Española de Inmunología Clínica, Alergología y Asma Pediátrica (SEICAP)

STUDY CENTRES: Imperial College London, UK & Niño Jesús Hospital, Madrid, Spain

NRES reference: 18/L0/1070

Protocol authorised by:

Name & Role

Date

Signature

AMENDMENT HISTORY

Amendment No.	Protocol Version	Date issued	Author(s) of changes	Details of Changes made
1	2.1	11 Dec 2018	[name] (CI)	
1. Change in maximum dose in Phase 1 updosing from 70mg to 60mg. Correspondingly, 70mg dose in Phase 2 updosing altered to 60mg.2. Removal of basophil activation test (under mechanistic assessments)3. Addition of [name] as co-PI in Madrid centre4. Minor typos corrected

PROTOCOL SYNOPSIS

Title	Improving the Safety of Oral immunotherapy for Cow's Milk Allergy
Abbreviated title	SOCMA study
Clinical Trials.gov number	NCT02216175
IRAS Number	174513
Sponsor R&D Number	18SM4569
HRA Ethics reference	18/L0/1070
Primary objectives	To evaluate the impact of a sublingual immunotherapy (SLIT) pretreatment on the safety of oral immunotherapy (OIT) in children with persistent IgE-mediated cow's milk (CM) allergy.
Secondary objectives	
1. To evaluate the safety and efficacy of CM-SLIT in children with IgE-mediated CM allergy.2. To assess whether the impact of SLIT pretreatment is dependent on sublingual exposure, or whether the same effect can be achieved through very low dose OIT.3. To evaluate predictors which can identify individuals likely to undergo successful desensitization.4. To assess the impact of CM immunotherapy on health-related quality of life.
Intervention	A two centre, parallel group, three arm, randomised placebo-controlled trial, comparing the safety and efficacy of OIT, with and without pretreatment with sublingual immunotherapy. At the end of each phase, efficacy of treatment will be assessed by double-blind, placebo-controlled food challenge (DBPCFC), to determine the change in threshold of reactivity for each participant.
Safety	Study visits will take place in a dedicated hospital paediatric research unit, by personnel qualified in the recognition and treatment of anaphylaxis, and observed for at least 60 minutes following a dose. All families will be provided with an Allergy Management Plan, prescription for rescue medication including adrenaline auto-injector devices, and appropriate training in the recognition and management of allergic reactions.
Patient group	Children and young people with a diagnosis of IgE-mediated cow's milk allergy between 6 - 17 years old. Target recruitment of 66 subjects
Sponsor	Imperial College London
Funding	J.P. Moulton Charity Foundation Sociedad Española de Alergología e Inmunología Clínica (SEAIC) Sociedad Española de Inmunología Clínica, Alergología y Asma Pediátrica (SEICAP)

Study Investigators

Joint Chief Investigators: [name], Imperial College London
[name], Imperial College Healthcare NHS Trust, London

Co-investigators: [name] [name], Niño Jesús Hospital, Madrid, Spain
[name], Niño Jesús Hospital, Madrid, Spain
[name], Niño Jesús Hospital, Madrid, Spain
[name] [name], Niño Jesús Hospital, Madrid, Spain

[name], Imperial College London
[name] [name], Hospital Universitario Ramón y Cajal, Madrid, Spain
[name], Hospital Universitario Ramón y Cajal, Madrid, Spain

Study sites

1. Imperial College London / Imperial College Healthcare NHS Trust
Site PIs: [name] & [name]
2. Niño Jesús Hospital, Madrid, Spain
Site PIs: [name] [name], & [name]

Study Coordination Centre

For general queries, supply of trial documentation, and collection of data, please contact:

Study Management Group

Joint Chief Investigators: [name], Imperial College London
[name], Imperial College Healthcare NHS Trust, London

Co-investigators: [name] [name], Niño Jesús Hospital, Madrid, Spain

Trial Steering Committee

Independent Chair: [name] (UK)
Independent Members: [name] (Spain)
[name] (UK)

Chief Investigator: [name] (UK)
Co-Investigator: [name] [name] (Spain)

Independent Data Monitoring Committee

Chair: [name] (UK)
Members: [name] (Spain)
[name] (UK)

Clinical Queries

Clinical queries should be directed to [name] who will direct the query to the appropriate person

Sponsor

Imperial College London is the research Sponsor for this study. For further information regarding the sponsorship conditions, please contact the Head of Regulatory Compliance at:

Joint Research Compliance Office

1. INTRODUCTION

1.1 BACKGROUND

Cow's milk allergy is the most common food allergy in young children, affecting up to 1 in 30 infants.¹ Allergic reactions are unpredictable, and have a major impact on the quality of life for the child and their family due to the potential for life-threatening allergic reactions (anaphylaxis) and the social/dietary restrictions needed to mitigate this risk.

There is no routine treatment available for CM allergy in the UK: day-to-day management involves avoidance of dairy foods and the availability of rescue medication (such as an adrenaline 'pen') in the event of an accidental reaction. Milk is ubiquitous in our diets, so avoidance is very difficult, especially as children grow older. In one study, CM was detected in 43% of the bakery products, with 21% containing sufficient CM to cause an allergic reaction in 10% of children with CM allergy.² Unsurprisingly, 2 in 5 children with CM allergy will have allergic reactions due to accidental reaction *every year*. While some will outgrow their milk allergy by school age, recent studies have shown that up to 50% will continue to remain allergic into their teens and beyond,¹ and this group are at greater risk of severe reactions and death. **Dietary avoidance is not a treatment – it is a management strategy.** Our aim is to develop a safe treatment for these young people.

One approach, used in some specialist centres in continental Europe and USA, is immunotherapy. Oral immunotherapy (OIT) involves administering very small but increasing amounts of CM daily for several months, and is effective for milk allergy, but causes significant reactions in some people. Milder reactions occur in 6 to 30% of doses, particularly in those with persisting CM allergy³. **We wish to test a novel approach to improving CM-OIT safety, to a level acceptable for standard clinical practice.**

Sublingual immunotherapy (SLIT), where the dose of CM is kept under the tongue for a few minutes, prior to swallowing, has a favourable safety profile. SLIT has revolutionised the field of immunotherapy to treat hay fever, particularly in children, allowing many more patients to access the treatment than previously due to improved safety and ease of updosing. Two studies have assessed SLIT for CM allergy,⁴ with a reassuring safety profile. **However, clinical efficacy was much more limited than for OIT – a major limitation of SLIT done in isolation.**

We propose to use SLIT pretreatment, at a higher dose than that previously used, followed by a standard OIT, to improve the safety and efficacy of OIT for CM allergy.⁵ Proof-of concept data exists relating to the use of SLIT pretreatment prior to peanut OIT in 9 children: the combination led to over 70% reduction in relative risk of systemic allergic reactions.⁶ A similar, well-powered study for CM allergy is thus warranted.

¹Turner PJ. Pediatr Allergy Immunol 2013; 24:624-6.

²Trendelenburg et al. Allergy. 2015 May;70(5):591-7.

³Vázquez-Ortiz M, Alvaro-Lozano M, Alsina L, et al. Clin Exp Allergy 2013; 43:92-102.

⁴Keet et al. J Allergy Clin Immunol. 2012; 129:448-55, 455.e1-5. De Boissieu et al. Allergy 2006; 61:1238-9.

⁵Vazquez-Ortiz & Turner. Pediatr Allergy Immunol. 2016;27(2):117-25.

⁶Narisety et al. J Allergy Clin Immunol. 2015; 135:1275-82.e1-6.

1.2 STUDY RATIONALE & JUSTIFICATION

We wish to formally assess, in a randomised, placebo-controlled study, whether SLIT pretreatment prior to OIT can improve the safety of oral desensitisation in children with persisting CM allergy. We will also evaluate whether the effect of SLIT is dependent on exposure via the sublingual route, or can be achieved when the equivalent dose is given orally (as very low dose OIT). We will assess the safety and efficacy of these approaches, and study the immunological mechanisms involved, our secondary aim being to develop clinically-useful predictors for identifying individuals likely to undergo successful desensitization.

STUDY HYPOTHESES:

1. Pretreatment with sublingual immunotherapy (SLIT) improves the safety of subsequent oral Immunotherapy (OIT) in children with cow's milk allergy.
2. The effect of pretreatment is dependent on exposure via the sublingual route: the same benefit is not obtained if pretreatment is directly swallowed.

2. STUDY OBJECTIVES

2.1 PRIMARY OBJECTIVE

- To evaluate the impact of SLIT pretreatment on the safety of OIT in children with IgE-mediated CM allergy.

2.2 SECONDARY OBJECTIVES

- To evaluate the safety and efficacy of CM-SLIT in children with IgE-mediated CM allergy.
- To assess whether the impact of SLIT pretreatment is dependent on sublingual exposure, or whether the same effect can be achieved through very low dose OIT.
- To evaluate predictors which can identify individuals likely to undergo successful desensitization.
- To assess the impact of CM immunotherapy on health-related quality of life.

3. STUDY DESIGN

The study is a two site, parallel group, three arm, randomised placebo-controlled trial, comparing the safety and efficacy of conventional OIT, with and without pretreatment with allergen immunotherapy delivered by either the sublingual or oral route (see Figure 1). At the end of each phase, efficacy of treatment will be assessed by double-blind, placebo-controlled food challenge (DBPCFC), to determine the change in threshold of reactivity for each participant. The study consists of 2 phases:

Phase 1 (duration 4-7 months): Participants will be randomised in a double-blind manner to intervention (active SLIT or low dose OIT or placebo) for 4-7 months, aiming for a 4 month period at maintenance dose.

Phase 2 (6 months duration): Open label intervention to assess the impact of the phase 1 intervention on subsequent safety of convention OIT to cow's milk.

[figure not shown]

Figure 1: CONSORT diagram for the SOCMA study.

[DBPCFC: double-blind, placebo-controlled food challenge; OIT: oral immunotherapy; SLIT: sublingual immunotherapy]

Summary of study components:

- Recruitment and eligibility screen:** CM-allergic subjects will be recruited from both our local patient population and through local paediatric allergy networks in London and Madrid.
- Baseline double-blind, placebo-controlled food challenge (DBPCFC) to CM:** This will confirm clinical reactivity to CM rather than sensitisation without clinical allergy, as it is unethical to undertake CM immunotherapy in children who are not clinically allergic to CM.
- Treatment Allocation and Phase 1:** CM-allergic children will be randomized 1:1:1 (using minimisation with weighted randomisation) to one of the following 3 arms, for 4-7 months (due to a target of 4 months duration at maintenance dose):

- i. Group S: SLIT, at a higher dose than that reported in previous studies [n=22]
- ii. Group O: "low dose OIT" using the same doses as SLIT but administered orally [n=22]
- iii. Group C: placebo control [n=22], half via the sublingual route, the remainder orally.
4. **Post phase 1 assessment:** All subjects will undergo a DBPCFC to CM to determine any change in threshold to CM following the Phase 1 intervention.
5. **Phase 2:** All subjects will be offered OIT using a conventional protocol for 6 months.
6. **Post phase 2 assessment:** All subjects will undergo an exit DBPCFC to CM to determine any change in threshold to CM. Blinding as to the phase 1 intervention will be preserved until after completion.

All participants will be advised on current best practice for CM allergy, i.e. CM avoidance (except for study doses) plus provision of rescue medication and training) for the duration of the study.

The impact of CM immunotherapy on HRQL will be assessed prior to, and after each phase in all subjects (and their parents), using validated questionnaires, with the final assessment 3 months after completing Phase 2.

3.1 STUDY OUTCOMES MEASURES

3.1.1 PRIMARY STUDY OUTCOME

The proportion of participants experiencing adverse events classified as mild non-transient symptoms or more severe (see table 9) during CM-OIT (phase 2), in those who have received SLIT pretreatment (group S) compared to placebo (group C).

3.1.2. SECONDARY STUDY OUTCOMES

- Proportion of participants experiencing adverse events classified as mild non-transient symptoms or more severe (see table 9) during CM-OIT (phase 2), in those who have received SLIT pretreatment (group S) compared to the equivalent SLIT dose orally during phase 1 (group O).
- Other safety outcomes in the different treatment groups (withdrawals due to intervention, anaphylaxis rate/adrenaline use)
- Efficacy defined at DBPCFC as the proportion of study participants experiencing:
 - i. No symptoms (or only mild transient symptoms as per table 9) to 8 grams CM protein (approx. 250mls fresh milk) ("Complete desensitisation")
 - ii. No symptoms (or only mild transient symptoms as per table 9) to at least 1.4 grams CM protein (approx. 45mls fresh milk) ("Partial desensitisation")
 - iii. At least a 10-fold increase in eliciting dose (defined as the lowest dose which elicits objective symptoms or signs at challenge).

Efficacy at 6 and 12 months will be compared across all treatment groups (including SLIT pretreatment) vs the equivalent dose administered orally without a sublingual phase (to address hypothesis 2).

- Immunological outcomes (titrated skin prick test, serum IgE) at baseline, 6 and 12 months.
- Change in health-related quality of life (HRQL) measures at 6, 12 and 15 months, as assessed by validated questionnaires (FAQLQ, FAIM, EQ-5D, self-efficacy) in study participants and their parents.

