- iii. The protocol already allows for an assessment for natural resolution of CM allergy, given the inclusion of a control group in Phase 1.

We will use an OIT protocol in Phase 2 that has been adapted from published and unpublished data relating to eliciting doses in children with CM allergy, as well as previous OIT protocols with favourable safety data. All updosings will take place under medical supervision. We therefore expect this protocol to have a satisfactory safety profile, even for those participants randomised to the placebo group in Phase 1.

The efficacy of treatment will be assessed by double-blind, placebo-controlled food challenge (DBPCFC) at the end of each phase, an established research tool in food allergy.⁸ We have chosen a daily maintenance dose of 4000mg CM protein (roughly equivalent to 120 ml or half a cup of milk), on the basis of previous reports that this amount is generally well-tolerated by subjects undergoing OIT on a daily basis, and it is also associated with a suggestion of efficacy. Our main efficacy outcome – "successful desensitization" or ability to tolerate 8000mg CM protein – has been chosen in agreement with previous studies to allow the intake of full milk servings following the intervention. This is expected to allow dietary liberalisation, potentially leading to a positive impact on health-related quality of life.

This is a two centre study: the procedures involved are complex and require intensive clinical assessment only available at specialist allergy centres with experience in food immunotherapy. The study design allows for a more efficient use of resources and promotes consistency in clinical management. The locations (in central London and Madrid) allow for the recruitment of patients from diverse geographical areas and ethnic background.

⁷Jay DC, Nadeau KC. Curr Allergy Asthma Rep. 2014; 14:473.

⁸Plaut M, Sawyer RT, Fenton MJ. Summary of the 2008 NIAID-US FDA Workshop on Food Allergy Clinical Trial Design. J Allergy Clin Immunol 2009;124:671-8.e1.

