For safety reasons, families will be asked to provide their child with a snack to eat one hour after the last dose has been given or the challenge has been stopped due to reaction. Participants will then be observed for a second hour prior to leaving the research unit. This is to avoid the possibility of the participant experiencing further symptoms outside the hospital when eating for the first time after challenge, something which has been noted in previous studies.

Entry and 6 month DBPCFC to Cow's Milk			
Dose	CM protein (mg)	Approximate equivalent volume of fresh CM (ml)	Minimum time interval after dose
1	0.5	0.015	60 mins at baseline DBPCFC, 20-30 mins for 6m DBPCFC
2	3	0.09	20-30 mins
3	10	0.3	20-30 mins
4	30	0.9	20-30 mins
5	100	3	20-30 mins
6	300	9	20-30 mins
7	1000	30	20-30 mins
8	3000	90	2 hours observation
Cumulative dose	4444	~130	
2 hours observation period following last dose to monitor for signs of reaction			

Table 2. Dosing protocol for DBPCFC to CM.

At the second visit of the baseline DBPCFC, the local investigator may elect to give participants who fail to react at either DBPCFC visit a single dose of cow's milk to a cumulative dose of 8 grams (approximately 250ml CM) in an open unblinded manner, 2 hours after the last challenge dose, to confirm tolerance.

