5.2.3 EXIT DBPCFC AT 12 MONTHS

The challenge will consist of up to nine consecutive, increasing doses of CM (or placebo) at 20-30 minute intervals, up to a cumulative dose of 8 gram CM protein, as shown in table 3.

Exit DBPCFC to Cow's Milk		
Dose	CM protein (mg)	Approx. volume of CM (ml)
1	0.5	0.015
2	3	0.09
3	10	0.3
4	30	0.9
5	100	3
6	300	9
7	1000	30
8	3000	90
9	3600	105
Cumulative dose	8044	250
2 hours observation period following last dose to monitor for signs of reaction		

Table 3. Dosing protocol for exit DBPCFC to CM.

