5.4 INTERIM POST-PHASE 1 ASSESSMENT (AROUND 6 MONTHS)

Subjects will be invited to undergo a DBPCFC to CM following completion of Phase 1 to again determine their threshold of reactivity to CM, according to Table 2 (Section 5.2.2). The pre-challenge assessment and challenge protocol are described in Section 5.2. Both challenge visits should take place with 28 days of each other. Subjects will also undergo repeat skin prick testing and HRQL assessments as described in section 5.8. Participants will continue their Phase 1 daily dosing until phase 2 is commenced.

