5.6.1 DBPCFC

All subjects will be invited to undergo a further DBPCFC to CM at approximately 12 months as described in 5.2. Both DBPCFC visits should take place between 24-30 weeks after commencing Phase 2 OIT. No OIT dose should be administered on the same day as a challenge visit. The purpose of this challenge is to determine the effect of the treatment in participants' threshold of reactivity. Successful desensitization will be defined as a negative outcome to a cumulative dose of 8g CM protein.

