7.2.2 ANALYSIS OF SECONDARY ENDPOINTS

The following secondary analyses will be performed using two-sided testing for non-parametric data at a $p<0.05$ level of significance:

- The incidence of adverse events experienced (including rate of withdrawals, and anaphylaxis/adrenaline use during updosing) between groups S, O and C in phases 1 and 2. Statistical differences will be determined using Fisher's exact test for proportions or using non-parametric tests for graded reactions. Logistic regression will be used to assess the influence of age, gender, asthma status and prior history of anaphylaxis amongst other factors on the incidence of adverse events.
- Efficacy defined at DBPCFC as the proportion of study participants experiencing:
 - No symptoms (or only mild transient symptoms as per table 9) to 8 grams CM protein (approx. 250mls fresh milk) ("Complete desensitisation")
 - No symptoms (or only mild transient symptoms as per table 9) to at least 1.4 grams CM protein (approx. 45mls fresh milk) ("Partial desensitisation")
 - At least a 10-fold increase in eliciting dose (defined as the lowest dose which elicits objective symptoms or signs at challenge)....at 6 and 12 months in the different treatment groups, using a two-sided Fisher's exact test at a $p<0.05$ level of significance.
- This will include a comparison of the efficacy of SLIT compared to the same dose administered orally without a sublingual phase (to address hypothesis 2), and its effect on the subsequent safety of OIT.
 - Immunological outcomes (titrated skin prick test, serum IgE) at baseline, 6 and 12 months.
 - Change in health-related quality of life (HRQL) measures at 6, 12 and 15 months, as assessed by validated questionnaires (FAQLQ, FAIM, EQ-5D) in study participants and their parents.
- Change in health-related quality of life (HRQL) measures at 6, 12 and 15 months, as assessed by validated questionnaires (FAQLQ, FAIM, EQ-5D) in study participants and their parents.
- Immunological outcomes (titrated skin prick test, serum IgE) at baseline, 6 and 12 months.
- The trend in CM-peptide binding over time as well as the potential influence of baseline peptide binding on the outcome of CM-IT will be assessed using a bioinformatics approach as in previous studies.²⁹

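### Secondary efficacy: 8 g tolerance cannot be observed at the 6-month challenge, and a child with a 1000 mg baseline eliciting dose cannot be shown to reach a 10-fold rise at either visit

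*Combined protocol and SAP*

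**What the plan says.** Section 3.1.2 defines efficacy by three proportions: tolerance of 8 g, tolerance of at least 1.4 g, and "At least a 10-fold increase in eliciting dose (defined as the lowest dose which elicits objective symptoms or signs at challenge". It then says: "Efficacy at 6 and 12 months will be compared across all treatment groups". Section 7.2.2 repeats the three criteria and applies a two-sided Fisher's exact test at the 5% level "at 6 and 12 months in the different treatment groups". Neither section assigns a criterion to one visit only.

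The challenges differ by visit:

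- **Baseline and 6 months.** Section 5.4 has the child "again determine their threshold of reactivity to CM, according to Table 2 (Section 5.2.2"). Table 2 has eight doses, the last 3000 mg, with a stated cumulative total of 4444 mg.
- **Open top-up to 8 g.** Section 5.2.2 provides it once: "At the second visit of the baseline DBPCFC, the local investigator may elect to give participants who fail to react at either DBPCFC visit". Nothing equivalent is given for 6 months.
- **Exit, 12 months.** Section 5.2.3 adds a ninth dose of 3600 mg and goes "up to a cumulative dose of 8 gram CM protein, as shown in table 3". Section 5.6.1 states: "Successful desensitization will be defined as a negative outcome to a cumulative dose of 8g CM protein".

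Inclusion criterion 3 (section 4.1) admits children who react at 1.44 g or less. Table 5 has a row for a tolerated baseline dose of 300 mg, so reaction at the next dose, 1000 mg, is foreseen.

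**The concern.** An endpoint can be compared at a visit only if that visit's challenge can show it.

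For the 8 g criterion at 6 months, the challenge stops well short of 8 g. Whoever runs section 7.2.2 must drop the test, report zeros in every arm, or substitute the 4.44 g challenge after the fact. Section 3.2 describes the main efficacy outcome as the "ability to tolerate 8000mg CM protein", so this choice should not be left open.

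For the 10-fold criterion, the obstacle is the ceiling of the dose range. A child who already tolerates 300 mg and reacts at 1000 mg leaves too little room above for a 10-fold rise to be seen. If such a child finishes the challenge without reacting, no eliciting dose exists under the definition in section 3.1.2, and the plan gives no rule for that case. At stake are one uninformative test and some loss of sensitivity in one secondary endpoint.

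**Working it through.** **Inputs.** Single doses come from Tables 2 and 3; the eligibility ceiling from section 4.1; 22 children per arm from section 3.

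**Reproducing the plan's totals.**

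- Table 2: 0.5 + 3 + 10 + 30 + 100 + 300 + 1000 + 3000 = 4443.5 mg (stated 4444).
- Table 3: 4443.5 + 3600 = 8043.5 mg (stated 8044).

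Both agree after rounding.

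**8 g at 6 months.** 4443.5 / 8000 = 55.5%, a shortfall of 8000 − 4443.5 = 3556.5 mg. At exit, 8043.5 mg exceeds 8000 mg, so the criterion is observable there. The 1.4 g criterion is observable at both visits, because the cumulative dose after the 1000 mg step is 1443.5 mg.

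**10-fold ceiling.** The largest recordable ratio is the top dose divided by the baseline eliciting dose.

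| Baseline eliciting dose (cumulative), mg | 6 months, single dose | 6 months, cumulative | Exit, single dose | Exit, cumulative |
|---|---|---|---|---|
| 100 (143.5) | 3000/100 = 30 | 4443.5/143.5 = 31.0 | 3600/100 = 36 | 8043.5/143.5 = 56.1 |
| 300 (443.5) | 3000/300 = 10.0 | 4443.5/443.5 = 10.02 | 3600/300 = 12 | 8043.5/443.5 = 18.1 |
| 1000 (1443.5) | 3000/1000 = 3.0 | 4443.5/1443.5 = 3.08 | 3600/1000 = 3.6 | 8043.5/1443.5 = 5.57 |

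Lower baseline doses have more room still. From 300 mg the criterion is only just attainable at 6 months. From 1000 mg it is unattainable on either scale. Even setting a single-dose baseline against a cumulative follow-up gives only 4443.5/1000 = 4.44 and 8043.5/1000 = 8.04.

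**A completed challenge.** A child who finishes without reacting has an eliciting dose above 3000 mg (6 months) or 3600 mg (exit). With a baseline of 300 mg or less, that bound already exceeds 10-fold. With a baseline of 1000 mg, it shows only more than 3.0-fold or 3.6-fold, so 10-fold status is unknown.

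**Size of the effect.** The documents do not give the number of 1000 mg reactors. Assume k per arm of 22, equal across arms. If they are counted as non-responders, the highest attainable rate is (22 − k)/22, and a difference among the other children shrinks by the same factor: 90.9% (k = 2), 81.8% (k = 4), 72.7% (k = 6).

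The power of the planned Fisher test (two-sided 0.05) follows. The response rates among the other children are assumed. Kept means k structural non-responders in an arm of 22; excluded means 22 − k per arm.

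| Rates in other children | k | Kept | Excluded |
|---|---|---|---|
| 50% v 10% | 2 | 72.8% | 74.2% |
| 50% v 10% | 4 | 65.8% | 66.8% |
| 50% v 10% | 6 | 57.8% | 58.1% |
| 80% v 40% | 2 | 58.0% | 65.0% |
| 80% v 40% | 4 | 46.5% | 61.4% |
| 80% v 40% | 6 | 34.2% | 50.5% |

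The loss runs from 0.4 points (57.8% v 58.1%, before rounding) to about 16 points (34.2% v 50.5%).

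**The case against.** The sponsor can say that the 8 g criterion plainly belongs to the exit visit: sections 5.2.3 and 5.6.1 place it there, and only that challenge is built to reach it. The intention is indeed clear, and it makes the point a small one. It does not correct sections 3.1.2 and 7.2.2, which both name 6 months.

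On the 10-fold criterion, the sponsor can say that a child who completes the challenge is right-censored, not a failure, so the cap is not fixed. That is correct. The cap applies only if such children are counted as non-responders, and the gap in the plan is the missing rule. The sponsor can also say that leaving out randomised children sits badly with the intention-to-treat statement in section 7.2. That is a fair reason to keep the all-participant result in view.

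A reader might infer two stronger points, which the documents do not support:

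- **That the 8 g and 10-fold criteria contradict each other.** A 1000 mg reactor could complete the exit challenge without a demonstrable 10-fold rise, while a child going from 3 mg to 30 mg has one. But one criterion is absolute and the other relative, and section 3.1.2 lists them as separate outcomes. Discordance between them is expected.
- **That the top eliciting-dose level in the minimisation (above 444 mg, section 5.3.1) is exactly the group that cannot respond.** Section 3.1.2 takes the lowest dose with an objective symptom or sign, and section 5.2.4.1 lets a challenge continue through minor findings. A child stopped at 1000 mg with an earlier minor objective sign at 300 mg has an eliciting dose of 300 mg and can reach 10-fold.

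**Conclusion.** Both parts hold, as a minor point on secondary endpoints.

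The 8 g comparison at 6 months cannot be carried out. Its result would be empty rather than misleading. This rests only on the dose tables and on the top-up being offered at baseline alone.

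A child with a baseline eliciting dose of 1000 mg, as section 3.1.2 defines it, cannot be shown to meet the 10-fold criterion at either visit. This takes the 1.44 g eligibility limit as the rounded cumulative dose through the 1000 mg step, which the 300 mg row of Table 5 supports. The cost depends on how many such children enrol, how they are scored and what the response rates are. The documents give none of these, and over the assumed ranges the cost goes from negligible to material.

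A reader might also infer bias between arms. The documents do not support that: eliciting dose is a minimisation factor, so the expected effect is lost sensitivity. The primary endpoint, the sample size, the 1.4 g endpoint and the 12-month 8 g endpoint are unaffected.

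**What to change.** Amend sections 3.1.2 and 7.2.2 as follows.

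1. Limit the 8 g endpoint to the 12-month exit challenge and keep the 1.4 g endpoint at both visits. Completion of the full 4.44 g challenge at 6 months may be reported descriptively.
2. For the 10-fold endpoint, where the baseline eliciting dose is 300 mg or less, score a follow-up challenge completed with no objective symptom or sign as at least 10-fold. The bounds above justify this at both visits.
3. Run the planned Fisher's exact test among those children. The subset is fixed by the baseline challenge, before randomisation. Show the all-participant result alongside, and tabulate the 1000 mg reactors separately.

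The cost is a few sentences. Challenges, doses, visits and data collection do not change. The downside is that one secondary endpoint is tested in a baseline-defined subset rather than in everyone randomised, which is why the all-participant result should stand next to it.
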